and overeating episodes without loss of control in BED is elevated negative affect and distress intolerance (i.e., the perceived inability to tolerate negative emotional states).³⁸⁻⁴² For example, one recent study found that among patients with BED, days characterized by high or increasing negative affect were associated with a greater likelihood of either a binge episode or an overeating episode without loss of control occurring on that day.⁴³ Although binge eating often begins as an impulsive attempt to regulate negative emotion^{39, 44-48}, persistent binge eating can lead to a compulsive use of eating as a way to regulate emotions^{45, 49} and reduce access to more adaptive coping strategies.^{45, 50} Ultimately, eating becomes one of very few “tools in the tool-kit” for reducing distress.⁵⁰ As seen in the figure above, elevated food reward sensitivity, overvaluation of shape and weight, and negative affect and distress intolerance directly and indirectly (e.g., by increasing rigid dietary restraint) contribute to binge eating, overeating episodes without loss of control, and an elevated BMI in patients with BED. These widely accepted maintenance factors for BED reflect areas where treatments can intervene to reduce overeating episodes with and without loss of control. However, existing behavioral treatments for BED fail to adequately address these shared maintenance factors.

A4. Cognitive behavioral therapy effectively reduces binge eating, but fails to improve weight.

The current gold-standard treatment for reducing binge eating in BED is Cognitive Behavioral Therapy (CBT)⁵¹, which uses cognitive and behavioral techniques to regularize eating, reduce dietary restraint, and alter the cognitive manifestations of BED.²⁹ CBT for BED is superior to other treatments in eliminating binge eating, with up to 60% of patients achieving full remission from binge eating.⁵¹ However, despite success in reducing binge eating, CBT fails to produce clinically significant weight loss in BED.⁵¹⁻⁵³

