Mind Your Health I. A previous NIH-funded project ([name], PI) assigned participants (n=128) to 30 sessions of ABBT or SBT for weight loss.¹⁵⁴ Attendance at ABBT groups was excellent ($M = 81.7\%$ of 30 sessions) and higher than in SBT ($M=73.9\%$) indicating that the acceptability of ABBT is high. When administered by clinicians with obesity treatment experience, percent weight loss was significantly higher in ABBT than SBT at post-treatment (13.2% vs. 7.5%; $p = .01$) and 6-month follow-up (11.0% vs. 4.8%; $p = .01$). Although BED patients were excluded, higher levels of depression, disinhibition and responsivity to food (characteristics typically elevated in BED) moderated the main effect of treatment. For example, among individuals with depression at baseline, 40-week weight losses were 18.2% for ABBT and 5.5% for SBT.

Mind Your Health II. A nearly completed NIH-funded project ([name], PI) assessed the long-term efficacy of ABBT versus SBT for overweight and obese adults. Participants (n=190) were randomly assigned to 25 sessions of ABBT or SBT. At post-treatment, ABBT yielded statistically and clinically significant greater percent weight loss ($M= 13.3\%$) compared to SBT ($M= 9.8\%$) and the superiority of ABBT was maintained at one-year follow-up.¹⁵⁷ Post-treatment retention rates (82.6% at 12 months) exceeded our target. Similar to Mind Your Health I, patients with BED were excluded from the study; however, patients with high food-specific impulsivity (which is elevated in BED¹⁵⁵) performed better in ABBT.¹⁵⁶

Project ENACT. Another NIH-funded project from our team ([name], Co-I) randomized 283 overweight and obese participants to receive 26 sessions of group-based SBT (with or without a focus on changing the home environment) or ABBT. As in the previous trials, patients with full-threshold BED were excluded from

treatment. However, patients with sub-clinical binge eating (defined as no more than three binge episodes in the three months before treatment) were included and preliminary results indicate greater weight loss in the ABBT condition ($M=11.58\%$) than the SBT ($M=9.71\%$) conditions for this subgroup.

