Primary Aim (Efficacy of ABBT). The study's data will consist of repeated assessments over time within randomized individuals within each treatment condition. Therefore, power calculations are dependent on both an expected difference between treatment arms as well as the clustering of the data (repeated observations within an individual with up to six repeated measures per participant within one of the two treatment conditions), resulting in a multilevel model structure. Using the method described by Raudenbush²⁵²⁻²⁵⁴ and implemented with the software Optimal Design, power calculations were made for this multilevel model structure. No results are available which directly compare the effect of ABBT and SBT on weight loss in BED patients. However, effect size can be predicted by deriving effect sizes from trials with elements similar to the proposed study, e.g., percent weight loss comparison between ABBT and SBT from the Mind Your Health II study (effect size at 12 months $d=0.39$) and percent weight loss and binge reduction comparison of CBT vs. SBT ($d=0.625$; 30% difference in binge reduction rates).⁶⁴ Based on previous studies, we aim to detect a clinically meaningful difference for both weight and binge eating frequency (3.5% weight loss between groups ($d=0.46$) and a difference in 4 binge eating episodes over the 4-week time period). Baseline covariates that can account for variability in the trial outcomes were taken into consideration in the power analysis. Given these assumptions, a sample size of 104 (52 for each group) is required for 80% power with the significant level of 0.05 and five assessment points, assuming the ratio of the variability of level-1 coefficient to the variability of level-1 residual is one. While allowing for up to 20% attrition, the proposed sample size of 130 is adequately powered to examine a clinically meaningful difference between treatment conditions for both percent weight loss and frequency of binge episodes. We believe this power estimate to be conservative given: 1) attrition estimates are greater than the team has achieved in similar weight control studies; and 2) missing values will be imputed using multiple imputation to maximize the number of the observations used to estimate models.

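### Protocol C11 attaches two effect sizes, 0.39 and 0.46, to the same 3.5-point weight-loss difference without a stated SD; if 0.39 applies unadjusted, the stated 80% power is about 66% at 104 analysed

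*Protocol*

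**What the plan says.** Protocol C11 (Power Analyses, Primary Aim) says that no direct comparison of ABBT with SBT on weight loss exists in patients with binge eating disorder (BED), so it borrows effect sizes from trials with similar elements. It names two sources:

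- the "percent weight loss comparison between ABBT and SBT from the Mind Your Health II study (effect size at 12 months $d=0.39";
- a "percent weight loss and binge reduction comparison of CBT vs. SBT", given as d = 0.625 together with a 30% difference in binge reduction rates.

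Citing previous studies, it then sets the clinically meaningful target for weight at "3.5% weight loss between groups ($d=0.46". It adds that baseline covariates were considered, without a figure, and concludes that "a sample size of 104 (52 for each group) is required for 80% power with the significant level of 0.05 and five assessment points". Allowing 20% attrition brings the total to 130. C11 calls this power estimate conservative.

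Protocol C1 reports the raw result of the earlier trial: "At post-treatment, ABBT yielded statistically and clinically significant greater percent weight loss ($M= 13.3\%$) compared to SBT ($M= 9.8" percent. It also fixes the timing of post-treatment in that trial: "Post-treatment retention rates (82.6% at 12 months) exceeded our target".

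**The concern.** The outcome (percent weight loss), the contrast (ABBT against SBT), the time point (12 months) and the raw difference (3.5 points) are the same in both places. Only the standardised effect differs. A larger d for the same raw difference means a smaller SD, and C11 does not say where a smaller SD comes from.

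The other cited effect cannot supply the increase for weight. Protocol A4 states that "CBT fails to produce clinically significant weight loss in BED", A5 describes behavioural weight loss as the most effective behavioural option for weight, and C6 rejects CBT as a comparator for this reason. On the protocol's own account, a CBT-versus-SBT contrast on weight favours what is the control arm here.

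At stake is the claim that 130 participants give adequate power for a 3.5-point difference. If the larger SD is nearer the truth, a non-significant weight result says less about a 3.5-point effect than C11 implies.

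**Working it through.** **Inputs.** From C11: target 3.5 points, d = 0.46 for the target, d = 0.39 for Mind Your Health II, 104 analysed (52 per arm), 80% power, alpha 0.05, 20% attrition, 130 enrolled. From C1: 13.3% and 9.8%. C11 does not state sidedness; two-sided is assumed.

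**1. Implied SDs.**
- Raw difference in the earlier trial: 13.3 − 9.8 = 3.5 points.
- SD from d = 0.39: 3.5 / 0.39 = 8.97.
- SD from d = 0.46: 3.5 / 0.46 = 7.61.
- Rounding does not reconcile them. Allowing for rounding, the first lies between 3.4 / 0.395 = 8.6 and 3.6 / 0.385 = 9.4, and the second between 3.45 / 0.465 = 7.4 and 3.55 / 0.455 = 7.8.

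**2. The plan's own figure.**
- The attrition step reproduces: 104 / (1 − 0.20) = 130.
- The 104 does not reproduce from the stated inputs. A plain two-sample comparison at d = 0.46 needs 2 × (1.960 + 0.842)² / 0.46² = 74.2, so 75 per arm (150 in total). With 52 per arm its power is Φ(0.46 × √26 − 1.960) = 65%.
- The repeated-measures method with five assessments and a variance ratio of one gives different totals depending on settings that C11 does not state. For linear change at unit frequency, the total is 166 if d is standardised by the SD of the change coefficient and 84 if by the total SD.
- About 104 appears only with further unstated choices, for example covariate R-squared of 0.30, or averaging five measurements with correlation about 0.62.

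**3. Rescaling the stated 80%.** Because the method cannot be rerun, take the stated 80% at 104 and d = 0.46 as the anchor. This assumes that both d values are on the same scale and that the noncentrality is proportional to d.
- Noncentrality at the anchor: 1.960 + 0.842 = 2.802.
- With d = 0.39: 2.802 × 0.39 / 0.46 = 2.375.
- Power at 104: Φ(2.375 − 1.960) = 66.1%.
- Power at 130: Φ(2.375 × √(130/104) − 1.960) = 75.7%.
- N for 80% power: 104 × (0.46 / 0.39)² = 144.7, about 145 analysed.
- Difference detectable with 80% power at 104: 0.46 × 8.97 = 4.1 points.

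**4. What would close the gap.**
- Covariates turn 0.39 into 0.46 if R-squared = 1 − (0.39 / 0.46)² = 0.28. Power then stays at 80%.
- In two-sample terms, going from d = 0.46 to 52 per arm still needs a further variance reduction of 1 − 52 / 74.2 = 30%. Starting from d = 0.39, where the requirement is 2 × 2.802² / 0.39² = 103.2 per arm, the total reduction needed is 1 − 52 / 103.2 = 50%. A covariate gain spent on raising d cannot be counted again in reaching 104.

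**The case against.** The best defence is that 0.46 is a planning value for a different population. Mind Your Health II excluded patients with BED, C11 cites it only as one example, and A5 reports much smaller weight losses in BED samples (6.95 kg against 13.51 kg), so its spread need not carry over. This stands as a reason not to treat 9.0 as the correct SD. It does not supply a source for 7.6: the documents give no SD for BED.

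The second defence is covariate adjustment. C11 says covariates were considered, and C10 lists demographics and baseline weight, dietary intake and physical activity as fixed effects. An R-squared near 0.28 would account for 0.46 in full. The documents do not rule this out, and repeated measures might supply the further reduction needed to reach 104. But C11 states 0.46 as the target first and mentions covariates afterwards as a separate assumption, which reads more naturally as an unadjusted 0.46. The weight model described in the SAP also names no baseline covariates. Neither point is proof.

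Third, 0.46 might be standardised within the multilevel model. In that case 3.5 / 0.46 is not an SD of percent weight loss, and the two values are not directly comparable. C11 does not say so.

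Finally, the SAP reports completed analyses with confidence intervals. Those intervals, not planned power, show which differences a null result excludes. That is right, and it limits the consequence to how the power claim is stated and used. It is also fair that 104 is a floor, because the planned mixed model uses partial data; hence the range up to 76%.

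**Conclusion.** The inconsistency holds: C11 gives two effect sizes for one 3.5-point difference, rounding does not explain it, and 0.46 has no stated SD, R-squared or derivation. Its size is conditional. If d = 0.39 applies and 0.46 is not already adjusted, power is about 66% at 104 analysed and about 76% at 130, and 80% power at 104 corresponds to about 4.1 points. These figures also rest on a two-sided 5% test, on the two d values sharing a scale, and on taking the plan's 80% as the anchor.

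A reader might infer more than this. The documents do not support saying that:

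- **the true power is 66%**, since an R-squared near 0.28 or a smaller SD in BED would leave it at 80%;
- **66% is the result of the plan's own method**, since that method's stated inputs do not give 104 and the figure is a rescaling;
- **the SD in this trial is 9.0**, since that value comes from a sample that excluded BED;
- **the CBT-versus-SBT value was used to raise 0.39 to 0.46**, since C11 does not say how 0.46 arose. The narrower point is that this value cannot support a larger ABBT effect on weight.

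**What to change.** State in C11, or in a dated clarification to it, the single SD and the covariate R-squared behind the 3.5-point target, with their sources and the scale on which d is standardised. If covariates explain the step from 0.39 to 0.46, show that the same gain is not used again in reaching 104.

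Unless a source for an SD of about 7.6 is given, restate the claim as about 66% (104 analysed) to 76% (130) power for 3.5 points, or as 80% power for about 4.1 points at 104. Stop describing the estimate as conservative, and do not cite the CBT-versus-SBT value in support of the weight effect. Interpret a null weight result from its confidence interval, with the restated figure beside it.

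The cost is wording and one recalculated figure. No extra participants are needed and the analysis does not change. The downside is a less favourable stated power.

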Participants will be screened by phone to assess preliminary eligibility. Phone screens will use questions from the Mini International Neuropsychiatric Interview (MINI)¹⁶³ to assess psychiatric comorbidity and will be conducted by trained graduate students, similar to procedures used successfully in our other NIH-funded trials. Those who appear eligible will attend an orientation session where they will receive detailed information about the study. At a subsequent clinic visit, eligibility will be verified, informed consent obtained, and the baseline assessment completed. The enrollment process will provide participants with an adequate opportunity

to determine whether the assessment burden and demands of the program are acceptable; this is expected to reduce attrition. After the baseline assessment, participants will be randomized to condition in blocks of 6, stratifying by BMI category (<30, 30-40, and >40), sex, race/ethnicity, and frequency of binge episodes.

C6. Therapy conditions. We decided to use SBT as our control condition given that weight loss is our primary outcome. We considered including CBT as an alternative control condition, but ultimately decided that CBT would be a sub-par control because this treatment does not directly encourage weight loss and consistently produces minimal to no weight loss for patients with BED.

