Primary Aim (Efficacy of ABBT). Analyses will be conducted via linear mixed effects models for longitudinal data, which increase power by fully exploiting the strong correlation in treatment outcomes of interests (i.e., primarily, percent weight loss and secondarily, percent binge frequency reduction) across time. Patterned covariance matrices as implemented in SAS/STAT PROC MIXED V9.2 will be used to evaluate between group differences for percent weight loss and percent binge reduction across the study as a whole, and at each assessment post-baseline.²²⁵ Separate variance components will be used to capture therapist and participant-within-therapist variation. The within-subject covariance matrix will be assumed common across study arms, with an exponential variance function to deal with heteroscedasticity and a continuous-time AR(1) correlation matrix to accommodate residual autocorrelation over the unequal-size time intervals between follow-ups. Outcomes at all six time points will be estimated jointly for maximum statistical efficiency in the presence of intermittent missingness and loss to follow-up. The model will include random effects for subject and time (with higher-order effects if needed to capture nonlinear change), and fixed effects for treatment arm, time by treatment interaction, demographic information, and baseline values of weight, dietary intake and physical activity. Time-specific covariate-adjusted contrasts will be used to compare outcome between groups.

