Mixed effects models were conducted for Primary Aim 1 (Efficacy of ABT) and Secondary Aim 2 (Between-Subjects Moderation) given nested data within subjects and group. The R “merTools” package was used for models predicting percent weight change and global eating disorder psychopathology change (Knowles et al., 2023), and the R “cplm” package was used for models predicting binge eating frequency change (due to zero-inflated distribution of percent binge eating change at post-treatment and follow-up) (Zhang, 2013). Models for percent weight and binge eating change included fixed effects for the interaction between linear or quadratic time effects and treatment condition (and baseline moderators for Secondary Aim 2). Only linear time effects were included in the models for global eating disorder psychopathology, since the quadratic time fixed effect did not significantly improve model fit. Model selection criteria (e.g., Aikaike information criteria, Bayesian information criteria) and significance testing were used to identify the random effects structure that best fit the model. For percent weight change, models included separate random effects for intercept and slopes of quadratic time effects nested within subjects. For binge eating frequency change, models included random effects for intercept nested within subjects. For global eating disorder psychopathology change, models included separate random effects for intercept and slopes of linear time effects nested within subjects. No differences in results were observed when treatment format delivery (i.e., telehealth vs. in-person groups) was included as a covariate; therefore, results without the inclusion of treatment format delivery as a covariate are reported. Statistically significant interactions were interpreted by plotting simple regression lines for each variable. For all linear mixed effects models, alpha was set at 0.05 and confidence intervals were obtained. Cohen’s f^2 effect size measures were estimated for group x time interaction using methods described by Selya and colleagues (Selya et al., 2012), with $f^2 \geq 0.02$, $f^2 \geq 0.15$, and $f^2 \geq 0.35$ representing small, medium, and large effect sizes, respectively.

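### The SAP weight and binge models list none of the protocol's baseline covariates or randomisation factors, although the power statement credits covariates, and its 80% cannot be reproduced from the stated inputs

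*Protocol*

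**What the plan says.** **Planned model (Protocol C10, Primary Aim).** Besides treatment arm and its interaction with time, the fixed effects are to include "demographic information, and baseline values of weight, dietary intake and physical activity". The comparison itself is specified: "Time-specific covariate-adjusted contrasts will be used to compare outcome between groups".

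**Randomisation (Protocol C5).** Participants are to be "randomized to condition in blocks of 6, stratifying by BMI category (<30, 30-40, and >40), sex, race/ethnicity, and frequency of binge episodes".

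**Power (Protocol C11, Primary Aim).** C11 states that "a sample size of 104 (52 for each group) is required for 80% power with the significant level of 0.05 and five assessment points", with a variance ratio of one, and adds: "Baseline covariates that can account for variability in the trial outcomes were taken into consideration in the power analysis". It does not name the covariates or give an R-squared. It calls the result conservative on two grounds: better retention than assumed, and multiple imputation of missing values.

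**Analysis as reported (SAP, second paragraph).** "Models for percent weight and binge eating change included fixed effects for the interaction between linear or quadratic time effects and treatment condition"; baseline moderators enter only for Secondary Aim 2. For the comparison of arms, "effect size measures were estimated for group x time interaction". Delivery format is the only covariate said to have been tried, and "results without the inclusion of treatment format delivery as a covariate are reported".

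**Elsewhere in the SAP.** The first paragraph reports no arm differences in age, sex, race or ethnicity, and therapist credentials. It also says that missing weights were singly imputed by a return-to-baseline rule. The third paragraph does name baseline covariates, but for the mediation models.

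**The concern.** Two things do not join up.

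First, the covariates in C10 and the stratification factors in C5 do not appear in the SAP's description of the weight and binge models, and neither do the adjusted visit-specific contrasts. The balance statement does not fill the gap. It does not mention baseline weight, BMI category, binge frequency, dietary intake or activity, and balance does not recover the precision that adjustment gives. If stratification factors are prognostic and are left out of the model, the standard error is overstated and the test errs on the conservative side.

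Second, the power statement takes credit for covariates that the listed analysis does not use, and gives no figure from which that credit could be judged. If the result is not significant, a reader cannot tell from C11 whether the trial could have detected the planned 3.5 percentage points. Nor does the SAP list the adjusted 12- and 24-month differences that C10 promised.

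**Working it through.** **1. What reproduces.** Attrition: 104 / (1 − 0.20) = 130, as stated.

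**2. Inputs.** From C11: 52 per arm, alpha 0.05 (two-sided assumed), 3.5 points at d = 0.46, d = 0.39 at 12 months in the earlier ABBT-versus-SBT trial, five assessments, variance ratio one. From C1 (Mind Your Health II): 13.3% against 9.8% weight loss, and 82.6% retention. Not given: estimand, SD, covariate R-squared. Clustering by therapy group is ignored below.

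**3. Implied SDs.** 3.5 / 0.46 = 7.6. In the earlier trial, 13.3 − 9.8 = 3.5, and 3.5 / 0.39 = 9.0. The 9.0 is an inference. It takes that trial's post-treatment difference as its 12-month result and its d as the raw standardised difference, and that trial excluded BED. Since 1 − (0.39/0.46)² = 0.28, d = 0.46 may itself already contain a covariate credit; the documents do not say.

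**4. Power without covariates.** Noncentral t, with noncentrality d × √(n/2) / √V.
- 12-month contrast: V = 1. At n = 52 and d = 0.46, noncentrality is 0.46 × √26 = 2.35.
- Five-visit average, d on the total SD: a ratio of one gives an intraclass correlation of 0.5, so V = 0.5 + 0.5/5 = 0.6 and noncentrality is 3.03.

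| | 12-month, d = 0.46 | 12-month, d = 0.39 | Five-visit average, d = 0.46 | Five-visit average, d = 0.39 |
|---|---|---|---|---|
| 104 analysed | 64% | 50% | 85% | 72% |
| 130 analysed | 74% | 60% | 92% | 81% |

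A linear growth model with d on the slope SD and five unit-spaced visits has V = 1 + 1/10 = 1.1 and gives 60% at d = 0.46.

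**5. What would restore 80% at 52 per arm and d = 0.46.** On the 12-month contrast, a covariate R-squared of about 0.31. In the growth model, covariates explaining about 40% of slope variance. One variant reaches 104 with no covariates: a random-intercept slope over six visits. That conflicts with the five assessments C11 states.

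**6. The conservative label.** 130 × 0.826 = 107, against 104, so the retention ground holds but adds little. Multiple imputation is not what the SAP used for weight.

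**7. What adjustment might gain.** These are illustrations from a linear random-slope model with visits at 1, 3, 6, 12 and 24 months and equal intercept, slope and residual variances.
- Main effects alone leave the treatment-by-time standard error unchanged.
- Main effects cut the 12-month standard error by 0 to 2% if the covariate acts on the slope only, and by roughly 7 to 15% if it also explains an assumed 15 to 30% of intercept variance in the same direction.
- For one slope-only covariate explaining an assumed 5, 15 or 30% of slope variance, covariate-by-time terms cut the treatment-by-time standard error by 2, 6 or 14%.
- Nine uninformative terms at 104 participants would inflate it by √(102/93) = 1.047, about 5%.

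**The case against.** Four points can fairly be made.

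**Silence is not omission.** The SAP says what the models included, not that they included nothing else. This stands, and it is why confirmation comes first in the fix. Against it, the SAP names baseline covariates for the mediation models and describes the efficacy models down to random effects and one rejected covariate.

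**Nothing is shown to be miscalculated.** A reader might infer from the 64% that 104 is too small and the trial underpowered. The documents do not support that. C11 says covariates were considered, a plausible R-squared restores 80%, the five-visit average exceeds 80% with none, and C10 plans comparisons over the whole study as well as at each visit. Because missing weights were imputed, the analysed number may also be nearer 130 than 104. What is missing is documentation of the inputs.

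**Following C10 to the letter may recover little.** C10 describes covariate main effects, which do not sharpen the treatment-by-time test. The gain at 12 months depends on how the covariates act. This stands. Neither document plans covariate-by-time terms, and their effect in the quadratic weight model or the cplm binge model has not been examined.

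**Readers do get intervals.** The SAP says confidence intervals were obtained and descriptives were produced by arm at each assessment. These inform readers more than retrospective power does, but they are not the adjusted visit-specific differences in C10. C10 does not itself list BMI category or binge frequency as covariates; the case for including them is that they were randomisation factors.

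**Conclusion.** The mismatch is real and should be fixed. As listed, the weight and binge analyses do not use the covariates in C10, the factors in C5 or the credit claimed in C11, and no adjusted contrast is listed at any visit. A reader might infer that the efficacy test is invalid. It is not: it is valid, probably conservative given stratified randomisation on prognostic factors, and less precise than the data could give.

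The 80% is unsupported as stated rather than wrong. At 104 participants and d = 0.46, unadjusted power runs from 64% (12-month contrast) to 85% (five-visit average), depending on an estimand that C11 does not state. These figures assume a two-sided test and no therapy-group clustering. The d = 0.39 figures also rest on the inferred SD of 9.0. The size of any precision gain cannot be fixed from the documents. Confidence is medium, mainly because the SAP's silence leaves open what was fitted.

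**What to change.** 1. Confirm whether the C10 covariates were in the fitted weight and binge models. If they were, list them in the SAP.
2. If they were not, add a supplementary analysis beside the current one, with the C10 covariates and the four randomisation factors as main effects. Take the list from C5 and C10, not from the results, and enter sex and race/ethnicity once. Report covariate-adjusted arm differences with intervals at 12 and 24 months, and state that the analysis was run after results were known.
3. Covariate-by-time terms may follow as a further analysis, disclosed as going beyond C10, since main effects alone do not sharpen the treatment-by-time test.
4. In the sample-size paragraph, state the estimand, the SD and its source, and the assumed R-squared. If power is restated, give both the 12-month and five-visit-average figures at 104 and 130 participants. Say that the SD of 9.0 is inferred and that d = 0.46 may already include a covariate credit.
5. Correct the basis for calling the estimate conservative: weight was singly imputed by return to baseline, not multiply imputed.

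The cost is one re-run on data already collected, an extra results row and a few degrees of freedom. The standard error would rise slightly if the covariates explain little. No further patients or visits are needed.
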